## 14 MEASURES: PATIENT-REPORTED OUTCOMES SURVEYS

### 14.1 Memorial Symptom Assessment Scale (MSAS) (Aims 1a, 3a, 4a)

The MSAS is a reliable and validated 32-item instrument that will be used to measure a number of pre-existing HCV-associated symptoms, potential treatment side effects during treatment, and change in symptoms and side effects post-treatment. The MSAS evaluates 32 prevalent symptoms or side effects that commonly occur in medical populations and during medical treatments. Patients will first indicate the presence or absence of the symptom/side effect, and if present, will rate the construct on severity, frequency and interference. An overall treatment toxicity score using all the items (referred to as TMAS) can be analyzed as well as descriptive statistics about each symptom/side effect.

### 14.2 PROMIS short forms (Aim 1b, 3a, 4b)

While the MSAS is capable of capturing a comprehensive set of many potential HCV-associated symptoms and toxic treatment side effects, the Patient-Reported Outcomes Measurement Information System® (PROMIS®) short forms will be used to precisely measure very specific constructs most common or salient to HCV and its treatment. The PROMIS short forms are a comprehensive set of highly reliable and validated tools that measure symptoms or treatment side effects across a wide range of chronic medical conditions. These constructs are not confounded by items measuring other symptoms or aspects of HRQOL. Each PROMIS short form includes a subset of items from a larger item bank that were the best performing items in content validity and reliability. PROMIS raw total scores are rescaled to a standardized T-score, which has a mean of 50 and standard deviation (SD) of 10 in the US general population.

#### 14.2.1 PROMIS short forms to measure HCV-associated symptoms

- PROMIS Fatigue -7a
- PROMIS Sleep Disturbance-8a
- PROMIS General Cognitive Concerns-8a
- PROMIS Pain Interference-8a
- PROMIS Belly/Liver Pain-6
- PROMIS Nausea/vomiting-4
- PROMIS Diarrhea-6
- PROMIS Irritability-5a
- PROMIS Depression-8a
- PROMIS Anxiety-4a

#### 14.2.2 PROMIS short forms to measure treatment side effects

- PROMIS Fatigue -7a
- PROMIS Sleep Disturbance-8a
- PROMIS Nausea/vomiting-4
- PROMIS Diarrhea-6
- PROMIS Irritability-5a
- PROMIS Anxiety-4a

#### 14.3 Headache Impact Test (HIT) to measure headache as a treatment side effect

Headaches are reported as adverse events in recent Phase III trials. The PROMIS measures do not include a short form to evaluate headache. We will measure headache as a side effect of treatment with the validated 6-item Headache Impact Test. Participants select responses from a 5-point Likert scale ranging from “Never” to “Always.” Higher scores are indicative of worse headaches and greater impact on the functioning.

#### 14.4 HCV-PRO to measure well-being and functioning (Aim 1c, 3b, 4d)

The HCV-PRO is a newly developed survey designed to assess the well-being and functional status of patients with HCV. It was developed in accordance with the PRO guidelines issued by the US FDA and demonstrated good reliability and convergent validity was moderate-high ( $r > 0.50$ ). HCV-PRO items measure physical, emotional and social functioning, productivity, intimacy, and perception of quality of life. Participants select responses from a 5-point Likert scale: 1=“all of the time” to 5=“none of the time”. A higher total score indicates higher functioning.

#### 14.5 Out of Pocket Costs survey to measure costs of treatment reported by patients (Aim 1e)

The personal cost of undergoing HCV treatment with new all-oral treatments is unknown, may vary considerably by insurance status and coverage, and may be a key consideration during patients’ decision-making. The literature describes the importance of measuring both direct and indirect costs of treatment. Patients will be asked to estimate the cost of 5 direct and 5 indirect costs associated with HCV treatment. Direct costs include: HCV medication co-pays, co-pays for prescriptions to manage side effects, over the counter remedies for side effects, doctor co-pays, blood draw copays. Indirect costs include: patient’s missed work/lost hourly wages, caregiver lost wages, childcare expenses, borrowing of money, gas and mileage to/from clinic.

#### 14.6 Voils Medication Adherence Survey (VMAS) to measure medication adherence (Aim 1f)

Medication adherence (how well patients take their medications every day as prescribed) and the reason for missed doses, may vary between treatment regimens, treatment durations and among patient subgroups. The VMAS consists of 3 items that evaluated the *extent* of adherence using a 5-point Likert scale from 1=None of the time to 5=All of the time. The 3 items assess how often participants missed doses, skip doses, or do not take doses over the past 7 days and are averaged into a single score shown to be reliable ( $\alpha = 0.84$ ). A

dichotomous variable will be created to categorize patients as 100% or <100% adherent. The VMAS has undergone qualitative testing in patients with HCV on antiviral therapy and is currently being validated in a HCV population on all-oral antiviral therapy.

#### **14.7 Sociodemographic Survey**

Participants will respond to sociodemographic questions at T1 baseline to characterize the study sample and explore as confounding variables: age, sex at birth, race, marital status, educational status, income level, living situation, employment status, and health coverage.

#### **14.8 Psychiatric and Substance Abuse History**

Patients with histories of psychiatric and addiction histories are important subgroups to evaluate, as they may have different outcomes compared to patients with psychiatric and addiction history. Participants will respond to 5 questions related to psychiatric history and 5 questions related to drug and alcohol use. Psychiatric questions include use of psychiatric medications, diagnosis of mental health problems, use of mental health treatment or services, and history of psychiatric hospitalizations. Addiction questions include frequency and amount of alcohol consumption, heavy drinking, and use of nonprescription drugs and prescribed drugs.

### **15 STATISTICAL ANALYSIS STRATEGY**

#### **15.1 Analysis plans registered in the master protocol document**

To help ensure reproducible results, these *a priori* plans specify detailed steps for the major inferential analyses along with guidelines for sensitivity analyses performed to assess the robustness of the major results to reasonable perturbations of the *a priori* assumptions, choices, and methods used. The plans also include (1) use of supportive analyses of subscales as an aid for understanding and interpreting the major analysis results, (2) a role for outcome-dependent exploratory analyses for hypothesis generation / refinement, and (3) necessary descriptive graphical and tabular methods used to characterize the participants, visualize the data and examine relationships among variables.

#### **15.2 Strategy for analysis of PRO change from baseline as a function of subgroup and/or treatment regimen**

Characterization of each subgroup or treatment regimen in terms of the interval-scale PRO variables will be based on N=1600 participants. Cirrhosis is expected in approximately 50% (n=800) of the subjects. Because subgroups, such as patients with cirrhosis, may have different experiences during and after treatment, estimation and inference characterizing the treatment regimens may be subgroup-specific (e.g., in manuscript #1 and #4). In contrast, primary analysis of the benefits of viral cure (SVR) may be all-inclusive without regard to treatment regimen (e.g., manuscript #2). The general model for change from baseline for each outcome variable (e.g., Total MSAS) may condition on covariates which include *cirrhosis status*, *age*, *race*, *sex at birth*, *treatment regimen*, the *cirrhosis-by-regimen* interaction, and the *baseline score* (e.g., Total MSAS). The models fitted will provide parameter estimates that will be used to obtain point estimates and confidence intervals (CI) to characterize each treatment regimen and/or each subgroup. A limited number of statistical hypotheses will also be tested. For binary PRO scales or subscales, a similar strategy will rely on logistic regression model methods.

#### **15.3 Supportive longitudinal analysis and interpretation of changes from baseline**

HCV-related symptom scores will be measured longitudinally. As an aid to interpretation of the primary results, and for purposes of generating new hypotheses, auxiliary longitudinal analyses of these repeated measures may also be explored.

Any increments from Baseline (T1) during treatment (T2/T3) will represent worsening of HCV-related symptoms or commencement of new onset treatment side effects. Similarly, decrements from Treatment (T2/T3) to 12-weeks post-treatment (T4) will represent amelioration or disappearance of symptoms. For any

symptoms remaining at T4, decrements from T4 to T5 will represent further healing. Thus for each individual the longitudinal trajectories of the scores represents that individual's history of waxing and/or waning of HCV-related symptoms. Secondarily, complementary analyses of each of the 32 symptoms will be used to investigate whether side effects that begin during treatment tend to resolve and to investigate the incidence of new symptoms or side effects that appear after treatment ends.

Treatment-related side-effects scores will also be measured longitudinally. Ideally, any increment from T1 to T2/T3 will be completely reversed by a decrement from T2/T3 to T4 or T5. Thus for each individual, the longitudinal trajectories of the scores represents that individual's history of waxing and/or waning treatment-related side-effects and HCV-related symptoms. These trajectories will be summarized descriptively via estimates of occasion-specific mean levels (with confidence intervals) and in terms of patterns of the trajectories represented, for example, by the proportion of patients for whom all treatment-related side-effects disappeared by T4/T5.

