## 15.7 Overview of Plans for Manuscript #3: Benefits of Achieving SVR

In the combined convenience sample of participants who achieve SVR (estimated to be ~1500), subgroups defined by achievement of SVR will be characterized and compared in terms of changes in PRO measures. The primary analyses for manuscript #3 will rely on a linear model for change from baseline for each PRO variable conditional on covariates which include *SVR status, cirrhosis status, age, race, sex at birth, treatment regimen, subgroup-by-regimen interaction, cirrhosis-by-regimen interaction, and the baseline PRO score*. Including the baseline PRO score as a covariate has several advantages for clarity of interpretation and improved precision of estimators of interest. The analysis will focus on point estimates and confidence intervals. PRO variables of interest in manuscript #3 are described here by aim:

Aim 3a1, MSAS. The outcome variable will be change from baseline (T1) to 3 months after end of treatment (T4). As an aid to interpretation, additional supportive tabulations for each of the 32 symptoms will be examined; e.g., change in side effects or pre-existing symptoms will be characterized in regard to change in raw frequency, severity and distress items.

Aim 3a2, PROMIS®. The primary analyses will focus on 10 symptom-specific PROMIS® T-scores and 1 HIT headache score. The outcome variable will be change from baseline (T1) to 3 months after end of treatment (T4). As an aid to interpretation of the main results, additional supportive tabulations for specific survey items will be examined.

Aim 3b, HCV-PRO. In the primary analysis, the outcome variable will be change from baseline (T1) to 3 months after end of treatment to determine benefit to well-being and functioning after cure (T4).

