## 15.8 Overview of Plans for Manuscript #4: Long-term Benefits / Harms

The primary analyses for manuscript #4 will rely on a linear model for change from baseline(T1) to one year post treatment (T5) for each PRO variable conditional on baseline covariates which include *cirrhosis status, age, race, sex at birth, treatment regimen, cirrhosis-by-regimen* interaction, and the *baseline PRO score*. Including the baseline PRO score as a covariate has several advantages for clarity of interpretation and improved precision of estimators of interest. The analysis will focus on point estimates and confidence intervals. As an aid to interpretation of the primary results, and for purposes of generating new hypotheses, auxiliary longitudinal analyses of the repeated measures will also be explored. The PRO variables of interest in manuscript #4 are described here by aim:

Aim 4a, MSAS. The outcome variable will be change from baseline (T1 to T5) in the total MSAS score. As an aid to interpretation, additional supportive tabulations for each of the 32 side effects will be examined; e.g., change in side effects/pre-existing symptoms will be characterized in regard to the raw frequency, severity and distress items.

Aim 4b, PROMIS. The primary analyses will focus on 10 symptom-specific PROMIS® T-scores and 1 HIT headache score. The outcome variable will be change from baseline (T1 to T5) in the total score. As an aid to interpretation of the main results, additional supportive tabulations for specific survey items will be examined.

Aim 4c, Pre-existing medical conditions. For each of several patient selected pre-existing conditions at baseline, we will descriptively examine which conditions stay the same, get worse, or get better one year after treatment ends. For the primary analyses, the outcome variable will be change from baseline (T1 to T5).

Aim 4d, HCV-PRO. The outcome variable will be change from baseline (T1 to T5).

Aim 4e, Cirrhosis differences. For each regimen we will evaluate the apparent effect of cirrhosis status on change from baseline (T1 to T5) for each of the outcome variables (4a, 4b, 4c, 4d). The results will be obtained from the models fitted for Aims 4a, 4b, 4c and 4d.

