### 15.11 Methods for Coping with Missing Data

The analysis plan relies on an extensive set of covariates measured at baseline. For purposes of estimation of the propensity score model, missing covariate values will be addressed via multiple imputation; furthermore, for each participant, the resulting multiplicity of propensity scores will be averaged together as proposed by Mitra and Reiter. The alternatives (e.g., average results from multiple outcome models) will be explored for purposes of sensitivity analysis. More generally, best practices for dealing appropriately with incomplete data, especially PROs, will depend on the documented causes of the missing, censored, or coarsened values. Every effort will be made to document the causes and to avoid incomplete data by capturing the PRO data even when the participant terminates treatment earlier than scheduled. Depending on the mechanisms which cause loss-to-follow-up for outcomes such as the MSAS at 1 year, multiple imputation methods may be appropriate.

Competing model-based methods will be examined for purposes of sensitivity analysis.

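### The primary T4 and T5 analyses are single-visit change-score models, and the plan commits to no primary method for participants who miss that survey

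*Combined protocol and SAP*

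**What the plan says.** For manuscript #4, Section 15.8 states that the primary analyses "will rely on a linear model for change from baseline(T1) to one year post treatment (T5) for each PRO variable". For manuscript #3, Section 15.7 states: "The primary analyses for manuscript #3 will rely on a linear model for change from baseline for each PRO variable", with the change running from T1 to T4. Both models include the baseline score, cirrhosis status, age, race, sex and regimen. Neither uses the scores collected in between, although Table 4 (Section 11.4) schedules MSAS, PROMIS, HIT and HCV-PRO at all five time points.

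Repeated-measures work is auxiliary in both places where it appears. Section 15.3 says that "auxiliary longitudinal analyses of these repeated measures may also be explored". Section 15.8 is firmer for T5: "auxiliary longitudinal analyses of the repeated measures will also be explored". In both, the stated purpose is interpretation and hypothesis generation.

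On missing data, Section 15.11 commits to multiple imputation only for covariates in the propensity-score model. For loss to follow-up in outcomes, with the one-year MSAS as its example, it says that, depending on the mechanism, "multiple imputation methods may be appropriate". It promises that competing model-based methods will be examined as sensitivity analyses, without naming them. Sections 15.2 and 15.12 base precision on all 1600 participants (about 1500 with SVR) and deduct nothing for missed T4 or T5 surveys.

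**The concern.** A linear model fitted to an observed change score leaves out anyone who lacks the second score. Someone who completed T1 to T4 but missed T5 contributes nothing to the primary T5 estimate. If those who feel worse at T4 are less likely to answer at T5, the remaining sample looks too well and long-term benefit is overstated. If those who feel better are the ones who leave, the error runs the other way.

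The baseline covariate deals with loss that depends on baseline. It does not deal with loss that depends on later scores related to the outcome given baseline: T2-T3 for the T4 analysis, T2-T4 for the T5 analysis. Those scores will be in the database. Section 15.1 says the a priori plans set out detailed steps for the major inferential analyses, yet for missing T4 and T5 outcomes no step is fixed. The primary estimate for more than ten scales would then rest on a method chosen after the missingness has been seen.

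**Working it through.** **1. Do the plan's figures assume complete follow-up?** Inputs (Section 15.12 and the Appendix, PROMIS): SD 10, serial correlation R = 0.50, two-sided alpha 0.05, detectable difference 1.40 at 80% power with 800 + 800.

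- SD of change = 10 × √(2(1 − 0.50)) = 10.
- Standard error of the difference = 10 × √(2/800) = 0.500. Power = Φ(1.40/0.500 − 1.96) = Φ(0.84) = 0.80. The plan's figure reproduces.
- Half-width = t(0.975, n−1) × 10 × √(χ²(0.80, n−1)/(n−1))/√n. This gives 0.51 at n = 1500 and 2.37 at n = 80 (stated: 0.52 and 2.37).

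The figures reproduce with every participant observed, so they make no allowance for loss.

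**2. Precision if people without T5 are dropped** (loss rates assumed). Power at 1.40:

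| Loss | n per group | Standard error | Power | Difference detectable at 80% |
|---|---|---|---|---|
| 10% | 720 | 0.527 | 0.757 | 1.48 |
| 20% | 640 | 0.559 | 0.707 | 1.57 |
| 30% | 560 | 0.598 | 0.649 | 1.67 |

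At 20% loss the half-width rises from 0.51 to 0.58 for N = 1500 and from 2.37 to 2.67 for N = 80.

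**3. Bias at T5.** The documents give no post-enrolment dropout rate or mechanism, so both are assumed. Normal scores were simulated with SD 10 and R = 0.50, and T5 loss was made to depend on T4 through a logistic model. The model was the completers' regression on baseline, evaluated at the full-cohort baseline mean.

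- Loss of 10-30%, odds of loss 1.35-1.8 per SD of T4 score: bias −0.08 to −0.43 points. With T4 added: −0.01 to 0.00.
- A wider five-visit set (odds 1.5-3 per SD, loss driven by T4 or by the T2-T4 mean): −0.10 to −0.87 at R = 0.50, and −0.15 to −1.43 if correlation falls from 0.8 between adjacent visits to 0.5.
- Loss driven by baseline alone: at most 0.02 in size.
- Imputation using T1-T4 scores: within 0.02 in every setting.

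**4. The evaluation point matters.** If means are taken at the completers' own baseline instead, loss driven by baseline alone gives a bias of 0.20 to 1.36. With R = 0.50 throughout, loss driven by post-baseline scores then gives almost none (within 0.01), because T1 and T5 are equally correlated with those scores and the errors cancel. With the falling correlation, T4-driven loss still leaves −0.08 to −0.54. Neither choice protects the completer analysis against every mechanism.

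**5. Size against the plan's thresholds.** PROMIS: 0.08/3 = 3% to 0.43/3 = 14% of the important difference. The same standardised bias on MSAS (SD 0.6, R = 0.50, important difference 0.10) is 0.008 × 0.6 = 0.005 to 0.043 × 0.6 = 0.026 points, or 5% to 26%.

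**6. Coverage.** Take a bias of 0.3 with 20% loss. In the five-visit set at R = 0.50 and 20% loss, T4-driven odds of 2 per SD gave 0.31 and odds of 1.5 gave 0.19, so 0.3 is an upper-end case. Coverage = Φ(1.96 − b/SE) − Φ(−1.96 − b/SE), with SE = 10/√(0.8N):

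| N | SE | b/SE | Coverage |
|---|---|---|---|
| 1500 | 0.289 | 1.04 | 82% |
| 800 | 0.395 | 0.76 | 88% |
| 160 | 0.884 | 0.34 | 94% |
| 80 | 1.250 | 0.24 | 94% |

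With a bias of 0.19, coverage at N = 1500 is 90% (b/SE = 0.66). These use the change-score SD of 10, as the plan's tables do. A smaller baseline-adjusted standard error would lower coverage somewhat for the same bias.

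**The case against.** A reader might infer that the plan prescribes a complete-case primary analysis. It does not. Omission is what the named model does by default, and Section 15.11 leaves imputation open for exactly this kind of loss and promises model-based sensitivity analyses. A reader might also infer that longitudinal analysis is wholly optional. That fits Section 15.3, but Section 15.8 commits to exploring it for T5, and Section 15.3 commits to occasion-specific means with confidence intervals. These points stand. They leave the gap open, because an auxiliary or sensitivity analysis does not supply the primary rule.

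It is also fair that the bias is small in clinical terms, rests on assumed dropout, and hardly affects regimen cohorts of 80-160, when characterising each regimen or subgroup is the primary objective. This limits the importance of the point. It remains relevant to the pooled SVR sample (about 1500), the Harvoni cohort (960) and the cirrhosis subgroups (about 800).

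The plan also works to prevent loss: assessment continues after early stopping (4.3.3, 15.11), there are three collection modes with escalation (11.1-11.3), and payments are higher at T4 and T5 (12). That may keep loss low, but it does not say how the remainder is analysed.

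**Conclusion.** The point holds as a gap in the primary analysis. The T4 and T5 models use one follow-up score, nothing commits the primary analysis to using T2-T4 scores, and no primary method for missing outcomes is named. If the default is followed, adjusted mean change at the full-cohort baseline is biased when loss depends on post-baseline scores.

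Under the assumed 10-30% loss and odds of 1.35-1.8 per SD, the T5 bias on PROMIS is about 0.1-0.4 points. That would not create or hide a 3-point change, but it can make the pooled intervals noticeably too confident. Stronger assumed dropout gives larger values.

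Two wider readings are not supported. Dependence on any earlier score is too broad, since loss that depends on baseline alone is handled by the covariate if means are evaluated at the full-cohort baseline. And the numbers apply to T5 only: the T4 argument has the same logic, but its size was not calculated. The change should be made, but it does not threaten the study's conclusions on clinically important differences.

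**What to change.** In Sections 15.7, 15.8 and 15.11, name one primary method for T4 and T5:

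- a likelihood-based repeated-measures model on T2-T5 scores with baseline, visit and the listed covariates, keeping covariate-by-visit terms to what the regimen-by-cirrhosis cells can support (several are expected to hold only 40-60 people); or
- multiple imputation of the missing T4 or T5 score from the T1-T4 scores available, SVR and treatment stop, followed by the planned linear model.

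State that adjusted means are evaluated at the full-cohort baseline. Keep the single-visit model as a sensitivity analysis, and add one for loss not at random, for example by shifting imputed scores over a stated range.

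The cost is analysis work only, since the scores and clinical fields are already scheduled for collection. Either method relies on data being missing at random given what was observed, and neither repairs loss that depends on the unseen T4 or T5 score itself. That is why the last sensitivity analysis is needed.
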